## 9.2 Responsibility for Analyses/In-house Blinding

The statistical analysis of the data obtained from this study will be the responsibility of the Clinical Biostatistics department of the Sponsor. This study will be conducted as a double-blind study under in-house blinding procedures. The official, final database will not be unblinded until medical/scientific review has been performed, protocol deviations have been identified, and data have been declared final and complete.

The Clinical Biostatistics department will generate the randomized allocation schedule(s) for study treatment assignment. Randomization will be implemented in an IRT. Blinding issues related to the planned interim analyses are described in Section 9.7.

## 9.3 Hypotheses/Estimation

Objectives and hypotheses of the study are stated in Section 3.

## 9.4 Analysis Endpoints

Immunogenicity and safety analysis endpoints that will be evaluated for within- and/or between-vaccine differences are listed below.

### 9.4.1 Immunogenicity Endpoints

A description of immunogenicity assessments is contained in Section 8.2. Immune responses will be measured for the 13 shared serotypes contained in V114 and Prevnar 13™ (1, 3, 4, 5,

6A, 6B, 7F, 9V, 14, 18C, 19A, 19F, and 23F) or all 15 serotypes contained in V114 (1, 3, 4, 5, 6A, 6B, 7F, 9V, 14, 18C, 19A, 19F, 22F, 23F, and 33F).

The primary immunogenicity analysis endpoint includes:

- Anti-PnPs serotype-specific IgG GMCs for the 13 shared serotypes contained in V114 and Prevnar 13TM at 30 days PD4

The secondary immunogenicity analysis endpoints include:

- Proportion of participants with anti-HBsAg concentration  $\geq 10$  mIU/mL at 30 days PD3 of V114 or Prevnar 13TM
- Anti-rotavirus IgA GMT at 30 days PD3 of V114 or Prevnar 13TM
- Anti-PnPs serotype-specific IgG GMCs for the 15 serotypes contained in V114 at 30 days PD3
- Anti-PnPs serotype-specific IgG response rates (proportion of participants with IgG  $\geq 0.35$   $\mu$ g/mL) for the 15 serotypes contained in V114 at 30 days PD3

The exploratory immunogenicity analysis endpoints include:

- Anti-PnPs serotype-specific IgG GMCs for the 15 serotypes contained in V114 prior to Dose 4
- Anti-HBsAg GMCs at 30 days PD3

#### 9.4.2 Safety Endpoints

A description of safety measures is contained in Sections 8.3 and 8.4. The analysis of safety results is described in Section 9.6.2.

Safety and tolerability will be assessed by clinical review of all relevant parameters including adverse events and postvaccination temperature measurements following any vaccination with V114 or Prevnar 13TM.

The safety analysis endpoints include:

- Proportion of participants with solicited injection-site AEs (redness/erythema, swelling, hard lump/induration, and tenderness/pain) from Day 1 through Day 14 following any vaccination with V114 or Prevnar 13TM

- Proportion of participants with solicited systemic AEs (irritability, drowsiness/somnolence, hives or welts/urticaria, and appetite loss/decreased appetite) from Day 1 through Day 14 following any vaccination with V114 or Prevnar 13™
- Proportions of participants with the broad AE categories consisting of any AE, a vaccine-related AE, an SAE, an AE which is both vaccine-related and serious, and discontinuation due to an AE, and the proportion of participants who died
- Proportion of participants with maximum temperature measurements meeting the Brighton Collaboration cut points Day 1 through Day 7 following any vaccination with V114 or Prevnar 13™

## 9.5 Analysis Populations

### 9.5.1 Immunogenicity Analysis Populations

The PP population will serve as the primary population for the analysis of immunogenicity data in this study. The PP population consists of all randomized participants without deviations from the protocol that may substantially affect the results of the immunogenicity endpoint(s). Potential deviations that may result in the exclusion of a participant from the PP population for all immunogenicity analyses include:

- Failure to receive primary infant series vaccination (V114/Prevnar 13™ Doses 1, 2, and 3) as per randomization schedule
- Receipt of prohibited medication or prohibited vaccine prior to study vaccination

Additional potential deviations that may result in the exclusion of a participant from the PP population for specific immunogenicity analyses (depending on the timepoint for analysis) include:

- Failure to receive V114, Prevnar 13™, RECOMBIVAX HB™, or RotaTeq™ according to vaccination schedule required at the timepoint for the analysis
- Failure to receive the scheduled doses of V114 or Prevnar 13™ (at least 28 days between Doses 1 and 2 and between Doses 2 and 3 [for PD3 and pre-dose 4 analysis], 12 months to 1 day prior to 16 months of age for Dose 4 [for PD4 PP analyses])
- Receipt of prohibited medication or prohibited vaccine prior to a blood sample collection
- Collection of blood sample at the timepoint for the analysis outside of the pre-specified window (as described in Section 1.3)

The final determination on protocol deviations, and thereby the composition of the PP population, will be made prior to the final unblinding of the database. Participants will be

included in the vaccination group to which they are randomized for the analysis of immunogenicity data using the PP population.

A supportive analysis using the Full Analysis Set (FAS) population will also be performed for the primary immunogenicity endpoints. The FAS population consists of all randomized participants who received all study vaccinations required at the timepoint for the analysis and have serology result. Participants will be included in the vaccination group to which they are randomized for the analysis of immunogenicity data using the FAS population.

### **9.5.2 Safety Analysis Populations**

Safety analyses will be conducted in the APaT population, which consists of all randomized participants who received at least 1 dose of study vaccination. Participants will be included in the group corresponding to the study vaccination they actually received for the analysis of safety data using the APaT population. This will be the group to which they are randomized except for participants who take incorrect study vaccination; such participants will be included in the vaccination group corresponding to the study vaccination actually received.

At least 1 temperature measurement obtained subsequent to study intervention is required for inclusion in the analysis of temperature.

## **9.6 Statistical Methods**

Statistical testing and inference for immunogenicity and safety analyses are described in Section 9.6.1 and Section 9.6.2, respectively. Unless otherwise stated, all statistical tests will be conducted at the  $\alpha=0.05$  (2-sided) level. Section 9.6.3 describes how demographic and baseline characteristics will be summarized.

### **9.6.1 Statistical Methods for Immunogenicity Analyses**

This section describes the statistical methods that address the primary and secondary immunogenicity objectives.

#### **Primary Endpoint**

The primary endpoint, anti-PnPs serotype-specific IgG GMC for 13 shared serotypes contained in V114 and Prevnar 13™ at 30 days PD4, is a descriptive endpoint. The primary endpoint will be summarized for each vaccination group. The confidence limits for IgG GMCs are the exponentiated confidence limits for the mean natural log concentrations, based on 1-sample t-distributions. Additionally, the estimation of serotype-specific IgG GMC ratios (between-group comparison) for 13 shared serotypes and its 95% CI will be calculated using the ANCOVA model utilizing the log-transformed antibody response as the response and vaccination group and stratification factor (hepatitis B vaccination status before enrollment = Yes, No) as covariates. The pairwise comparisons for primary objective include Group 2 vs Group 1; Group 3 vs Group 1; and Group 4 vs Group 1. The same approach will be used to

evaluate the secondary endpoint, serotype-specific IgG GMC ratios comparing Group 5 vs Group 1.

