AE Monitoring	X	X	X	X	X	X	X	X	X	X	X	AEs (serious and non-serious) are to be reported from Days 1 through 14 following each vaccination. SAEs and deaths are to be reported throughout the duration of an individual's study participation.
Immunogenicity Procedures												
Serum for Immunogenicity Assays (Including Retention Serum)							X	X		X		Blood samples must be collected before vaccination.

Study Period	Intervention										Follow-up	Comments
	1	TC	2	TC	3	TC	4	5	TC	6	TC	
Scheduled Time:	Age: ~2 months Dose 1	Day 15 after Dose 1	Age: ~4 months Dose 2	Day 15 after Dose 2	Age: ~6 months Dose 3	Day 15 after Dose 3	~1 month after Dose 3	Age: ~12 to 15 months Dose 4	Day 15 after Dose 4	~1 month after Dose 4	~6 months after Dose 4	
Visit Window a :	≥42 days of age to ≤90 days of age	Day 15 to Day 19 Post dose 1	4 months of age to 1 day prior to 5 months of age	Day 15 to Day 19 Post dose 2	6 months of age to 1 day prior to 7 months of age	Day 15 to Day 19 Post dose 3	Day 28 to Day 42 Post dose 3	12 months of age to 1 day prior to 16 months of age	Day 15 to Day 19 Post dose 4	Day 28 to Day 42 Post dose 4	Day 166 to Day 194 Post dose 4	
Future Biomedical Research												
Collect Buccal Swabs for Future Biomedical Research	X											Buccal swab DNA samples for analysis should be obtained prior to the vaccination at Visit 1, on randomized participants only, or at a later date as soon as the informed consent is obtained.

a For calculating the visit windows, the day of vaccination is considered Day 1. To calculate visit windows for subsequent vaccinations, confirm subject date of birth and ensure the age of the subject will fall within the appropriate age range for each study visit.

ACIP = Advisory Committee on Immunization Practices; AE = adverse event; DNA = deoxyribonucleic acid; eVRC = electronic Vaccination Report Card; SAE = serious adverse event; TC = telephone contact; US = United States

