## 3 HYPOTHESIS, OBJECTIVES, AND ENDPOINTS

The following hypotheses, objectives and endpoints will be evaluated in healthy infants administered V114 or Prevnar 13™ in 1 of 5 intervention groups:

**Group 1:** Prevnar 13™ → Prevnar 13™ → Prevnar 13™ → Prevnar 13™

**Group 2:** Prevnar 13™ → Prevnar 13™ → Prevnar 13™ → V114

**Group 3:** Prevnar 13™ → Prevnar 13™ → V114 → V114

**Group 4:** Prevnar 13™ → V114 → V114 → V114

**Group 5:** V114 → V114 → V114 → V114

Objectives	Endpoints
Primary	

 
Objective: To evaluate the safety and tolerability of complete V114 (Group 5) and mixed Prevnar 13™/V114 dosing schedules (Groups 2, 3, and 4) compared with a complete dosing schedule of Prevnar 13™ (Group 1) with respect to the proportion of participants with adverse events (AEs).
 
	
Following any vaccination with V114 or Prevnar 13™:
 
 
Solicited injection-site AEs from Day 1 through Day 14 postvaccination
 
Solicited systemic AEs from Day 1 through Day 14 postvaccination
 
Vaccine-related serious adverse events (SAEs) through completion of study participation
 

 
Objective: To evaluate the anti-pneumococcal polysaccharide (PnPs) serotype-specific Immunoglobulin G (IgG) Geometric Mean Concentrations (GMCs) at 30 days following Dose 4 for participants administered mixed dosing schedules of Prevnar 13™/V114 (Groups 2, 3, and 4) compared with participants administered a complete dosing schedule of Prevnar 13™ (Group 1).
 
	
 
Anti-PnPs serotype-specific IgG responses for the 13 shared serotypes contained in V114 and Prevnar 13™ at 30 days postdose 4 (PD4)
 

Secondary	

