#### **8.1.8.1 Timing of Dose Administration**

V114 or Prevnar 13™ will be administered as indicated in Section 1.3. Other pediatric vaccines will be administered concomitantly on the same day as study vaccine according to the recommended schedule (Section 6.5). All participants will be observed for 30 minutes following each vaccination for any immediate reactions. This observation must be performed by blinded site personnel for V114 and Prevnar 13™ (Section 1.3 and Section 6.3.3).

Participants must be afebrile for at least 72 hours prior to vaccination.

Blood samples must be collected before study vaccination, when applicable.

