For the other secondary endpoints and exploratory continuous descriptive endpoints ;anti-PnPs serotype-specific IgG GMCs at 30 days PD3 of V114 or Prevnar 13TM and prior to Dose 4 and anti-HBsAg GMCs at 30 days PD3, each vaccination groups will be evaluated separately. The point estimates will be calculated by exponentiating the estimates of the mean of the natural log values and the within-group CIs will be derived by exponentiating the CIs of the mean of the natural log values based on the 1-sample t-distribution. For the dichotomous endpoints that immune responses meet threshold value as defined in the objectives , the within-group CIs will be calculated based on the exact method proposed by Clopper and Pearson[Collett, D. 1999].

Reverse Cumulative Distribution Curves for IgG concentrations at 30 days PD3 and 30 days PD4 will be graphically displayed by serotype.

A detailed analysis strategy for immunogenicity endpoints is listed in [Table 6](#).

Table 6 Analysis Strategy for Immunogenicity Variables

Endpoint/Variable (Description, Time Point)	Primary vs. Supportive Approach †	Statistical Method ‡	Analysis Population	Missing Data Approach
Primary Endpoint				
Anti-PnPs IgG GMCs for the 13 shared serotypes contained in V114 and Prevnar 13 TM at 30 days PD4	P	ANCOVA § (estimate, 95% CI)	PP	Missing data will not be imputed
	S		FAS	
Secondary Endpoint #1/Hypothesis (H1)				
Proportion of participants with anti-HBsAg concentration $\geq 10$ mIU/mL at 30 days PD3 of V114 or Prevnar 13 TM	P	Stratified Miettinen and Nurminen ¶ (estimate, 95% CI, p-value)	PP	Missing data will not be imputed
	S		FAS	
Secondary Endpoint #2/Hypothesis (H2)				
Anti-rotavirus IgA GMT at 30 days PD3 of V114 or Prevnar 13 TM	P	ANCOVA § (estimate, 95% CI, p-value)	PP	Missing data will not be imputed
	S		FAS	
Other Secondary Endpoints				
Anti-PnPs IgG GMCs for the 15 serotypes contained in V114 at 30 days PD3	P	Descriptive Statistics (estimate, 95% CI)	PP	Missing data will not be imputed
Proportion of participants with anti-PnPs IgG $\geq 0.35$ $\mu$ g/mL for the 15 serotypes contained in V114 at 30 days PD3	P	Descriptive Statistics (estimate, 95% CI  )	PP	Missing data will not be imputed

† P = Primary approach; S = Supportive approach.

‡ Statistical models are described in further detail below:

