§ ANCOVA model with log-transformed antibody responses as response variable and vaccination group, and stratification factor (hepatitis B vaccination status before enrollment = Yes, No) as covariates.

¶ Within group summaries provided using exact method proposed by Clopper and Pearson.

|| Stratification factor (hepatitis B vaccination status before enrollment = Yes, No).

CI = confidence interval; FAS = Full Analysis Set; GMC = Geometric Mean Concentration; GMT = Geometric Mean Titer; HBsAg = Hepatitis B surface antigen; IgA = Immunoglobulin A; IgG = Immunoglobulin G; PD = postdose; PnPs = pneumococcal polysaccharide; PP = Per-Protocol

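### Should the postdose 4 comparison of Group 2 with Group 1 be adjusted for the IgG measured just before Dose 4?

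*Combined protocol and SAP*

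**What the plan says.** For the primary immunogenicity endpoint, Section 9.6.1 specifies an "ANCOVA model utilizing the log-transformed antibody response as the response and vaccination group and stratification factor", the factor being hepatitis B vaccination before enrolment. The footnote to Table 6 gives the same model: an "ANCOVA model with log-transformed antibody responses as response variable and vaccination group, and stratification factor". The primary contrasts are Groups 2, 3 and 4, each against Group 1. Section 9.8 states that the primary immunogenicity objective carries no formal hypothesis test.

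Group 2 follows the sequence "Prevnar 13™ → Prevnar 13™ → Prevnar 13™ → V114" (Section 3). Group 1 receives Prevnar 13 throughout, so the two differ only at the fourth dose. Serum is taken at Visits 4, 5 and 6 (Section 8). At Visit 5 it precedes the injection: "Blood samples must be collected before vaccination" (Section 1.3), and again "Blood samples must be collected before study vaccination, when applicable" (Section 8.1.8.1). Section 8.2 has the sera assayed for all 15 serotypes.

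The pre-dose 4 result has its own exploratory endpoint in Section 9.4.1: "Anti-PnPs serotype-specific IgG GMCs for the 15 serotypes contained in V114 prior to Dose 4". Section 9.6.1 analyses it within groups only: "prior to Dose 4 and anti-HBsAg GMCs at 30 days PD3, each vaccination groups will be evaluated separately". Section 4.2.1.1 gives its purpose, which is to describe persistence and the anamnestic response.

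**The concern.** A covariate that treatment cannot have affected and that predicts the outcome usually narrows a confidence interval at no cost in bias. For Group 2 against Group 1, pre-dose 4 IgG of the same serotype appears to be such a covariate. It is measured before the only point at which the two regimens part, in blood that is drawn and assayed anyway.

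Section 9.9.1 describes the sample size for the primary immunogenicity objective through interval width alone (Table 8). A reader could therefore conclude that the plan gives up precision in the one quantity by which it judges that objective. At stake would be wider intervals than necessary for 13 of the 39 primary ratios (13 serotypes × 3 contrasts), namely those that isolate a switch at the toddler dose.

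**Working it through.** **1. Reproduce Table 8.** Inputs from Section 9.9.1: 180 × 0.75 = 135 evaluable per group, and SDs of 0.5 to 2 on the natural log scale. The interval is ratio × exp(±t × SD × √(2/135)), with t on 268 degrees of freedom = 1.9689 and √(2/135) = 0.1217. At ratio 1:

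- SD 1: half-width 1.9689 × 1 × 0.1217 = 0.240, giving (0.79, 1.27).
- SD 1.5: half-width 0.359, giving (0.70, 1.43).

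All 20 intervals in Table 8 agree to two decimals.

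**2. Is the covariate legitimate for this pair?** Yes. Nothing assigned differs between Groups 1 and 2 before Visit 5. It is a pre-switch value, not a baseline at randomization, so this also assumes that blinding holds and that retention up to Dose 4 is similar in the two groups. With 135 per group, SD 1, r = 0.5 and a true ratio of 0.80, simulation gave a mean adjusted ratio of 0.80, 94.5% coverage and 0.87 of the unadjusted width.

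**3. Can it be used for the other contrasts?** No. Groups 3, 4 and 5 have already received V114 by Visit 5. If that earlier exposure is assumed to shift pre-dose 4 IgG by a ratio of 0.7, the same simulation gives an adjusted ratio of 0.96 instead of 0.80, and coverage of the true ratio falls to 60%. A single model for all contrasts therefore has to leave the covariate out, as the plan does.

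**4. How much could it gain?** Let r be the within-group correlation of log pre-dose 4 and log postdose 4 IgG. The documents do not give it, so a range is shown. With no missing values, the log-scale width is multiplied by √(1 − r²). At SD 1.5 and ratio 1:

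| r | √(1 − r²) | Interval |
|---|---|---|
| 0 | 1.000 | (0.70, 1.43) |
| 0.1 | 0.995 | (0.70, 1.43) |
| 0.2 | 0.980 | (0.70, 1.42) |
| 0.3 | 0.954 | (0.71, 1.41) |
| 0.5 | 0.866 | (0.73, 1.37) |
| 0.7 | 0.714 | (0.77, 1.29) |

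**5. Against the interval actually planned.** The factor in step 4 compares two models fitted to the same two groups. The plan does not say whether its ANCOVA pools all five groups. If it does, the primary interval has 5 × 135 − 6 = 669 degrees of freedom (t = 1.9635), and a two-group adjusted model has 270 − 4 = 266 (t = 1.9689). That is a handicap of 1.9689/1.9635 = 1.0028, before the small cost of estimating the covariate's slope. Simulated mean width ratios, adjusted two-group over pooled primary (2,000 trials per setting, SD 1.5, an assumed 70% with prior hepatitis B vaccination):

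| r | No missing covariate | 10% missing, with indicator |
|---|---|---|
| 0 | 1.005 | 1.007 |
| 0.1 | 0.999 | 1.003 |
| 0.2 | 0.984 | 0.989 |
| 0.3 | 0.960 | 0.965 |
| 0.5 | 0.869 | 0.886 |
| 0.7 | 0.717 | 0.752 |

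Break-even is at r of about 0.10, or 0.12 with 10% missing. With no missing values, the adjusted interval is the narrower one in 44% of trials at r = 0, where the covariate carries no information, in 51% at 0.1 and in 67% at 0.2. At low r, much of any apparent narrowing is therefore chance variation in the residual variance.

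If infants without a pre-dose 4 result are dropped instead, the factor from step 4 becomes √((1 − r²)/(1 − f)) for a missing fraction f. At r = 0.3 and f = 0.10 that is √(0.91/0.90) = 1.006, so the gain is lost.

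**6. What would change in the trial's results?** The 39 primary intervals stay as planned; 13 × 1 = 13 are added. H1 and H2 are postdose 3 endpoints and are untouched, as are their stated powers of about 96% and 98%. The primary objective has no margin that a narrower interval could clear.

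**The case for a change.** The best argument for acting is that the covariate is free and sound for this pair, that interval width is the plan's own yardstick, and that a model chosen after unblinding would count as post hoc. If r were 0.5 or more, the interval would be clearly tighter. All of this stands as an argument that the analysis is permissible and might be informative.

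It does not show that the plan is deficient. Nothing in the documents puts r at the useful end of the range. The extra analysis also needs several choices on which statisticians could reasonably differ:

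- **Which measurement.** Postdose 3 IgG also precedes the switch, and the documents do not show which of the two predicts better.
- **Missing values.** They could be handled with an indicator or by dropping infants.
- **Which samples count.** Section 9.5.1 sets different dose-timing rules by timepoint: "between Doses 2 and 3 [for PD3 and pre-dose 4 analysis], 12 months to 1 day prior to 16 months of age for Dose 4".
- **How to read the result.** If the primary model is pooled, a two-group adjusted fit changes both the variance estimate and the covariate set. A difference in width could be credited to the covariate only with an unadjusted two-group fit alongside.

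One of three parallel contrasts would then carry a second estimate that is not directly comparable with those for Groups 3 and 4.

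**Conclusion.** The concern does not hold. It is true that no planned model uses pre-dose 4 IgG as a covariate, and that for Group 2 against Group 1 it could be used. But the planned ANCOVA is valid without it, treats the three primary contrasts alike, and avoids an adjustment that could bias two of them. The most that adjustment offers is 13 supplementary intervals. Against a pooled primary model these would run from about 0.5% wider on average (r = 0) to about 28% narrower (r = 0.7, width ratio 0.717), with no missing covariate values.

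These sizes rest on assumed values of r, on 135 evaluable infants per group and on the SDs in Table 8. The conclusion does not depend on r: even a large gain would leave every primary interval, hypothesis and power statement as it is. Adding the supportive model is optional, and omitting it is no error.

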## **Secondary Endpoints**

### **Secondary Endpoint #1/Hypothesis (H1)**

For the hypothesis (H1), the proportion of participants with anti-HBsAg concentration  $\geq 10$  mIU/mL at 30 days PD3 from participants administered primary infant series dosing schedule V114 (Group 5) concomitantly with RECOMBIVAX HBTM will be compared to participants administered a complete primary infant series dosing schedule of Prevnar 13TM (Group 1 + Group 2) concomitantly with RECOMBIVAX HBTM at 30 days PD3 of V114 or Prevnar 13TM via the following non-inferiority hypotheses:

$$H_0: p_1 - p_2 \leq -0.10 \text{ versus}$$
$$H_1: p_1 - p_2 > -0.10$$

Where  $p_1$  is proportion of participants with anti-HBsAg concentration  $\geq 10$  mIU/mL at 30 days PD3 for Group 5 and  $p_2$  is proportion of participants with anti-HBsAg concentration  $\geq 10$  mIU/mL at 30 days PD3 for Group 1 + Group 2.

RECOMBIVAX HBTM administered concomitantly with V114 is non-inferior to RECOMBIVAX HBTM administered concomitantly with Prevnar 13TM if the lower bound of the 2-sided 95% CI for the between-treatment difference between Group 5 vs (Group 1 + Group 2)  $> -0.10$ . The proposed 10 percentage point margin is the same as those observed in previous Merck vaccine concomitant use studies evaluating similar antigens. The stratified Miettinen and Nurminen approach will be used for the analysis of this endpoint. The stratification factor is hepatitis B vaccination status before enrollment (Yes, No) [Miettinen, O. and Nurminen, M. 1985].

